#### 4.0 Test Schedule

##### 4.1 MK-3475 single-agent therapy for both CLL (Arms A and C) and B-NHL (Arm B)

Tests & Procedures	Active Monitoring Phase					
	Days Prior to Registration (Screening phase) ≤30 days	≤14 days	Prior to each cycle, beginning with cycle 2 	Response Evaluation  at 3, 6, and 12 months of therapy	Observation (every 90 days ± 14 days)	At time of progression 
Complete medical history	X					
Adverse event assessment		X	X 	X	X	X
Physical exam, including weight, and vital signs, ECOG PS		X	X 	X	X	X
Height		X				
Tumor measurement by physical exam (CLL/SLL arm only) 		X 	X 	X	X	X
Peripheral blood immunophenotyping by flow cytometry	X 					
CBC with differential and reticulocytes 		X	X 	X	X	X
Serum pregnancy test		X 				
Peripheral smear		X				
Chemistry group (SGOT [AST], SGPT [ALT], total bilirubin[T-Bil], serum creatinine, alkaline phosphatase, direct bilirubin only when T-Bil elevated)		X	X	X	X	X
Uric acid, phosphate, calcium, potassium, sodium		X				
HBsAg, Hep C Ab, HB core antibody		X				
IGHV (CLL/SLL arm only)	X 					
Bone marrow biopsy/aspirate	X 			X 		
Serum protein electrophoresis (SPEP)		X 		X 		

		Active Monitoring Phase				
Tests & Procedures		Days Prior to Registration (Screening phase)	Prior to each cycle, beginning with Cycle 2 	Response Evaluation  : at 3, 6, and 12 months of therapy	Observation (every 90 days ± 14 days)	At time of progression 
		≤30 days	≤14 days			
Beta-2-microglobulin (CLL/SLL arm only)		X				
Serum quantitative immunoglobulins (IgG, IgA, IgM)		X 	X (IgM only) 	X 		X 
Coombs test (monospecific direct coombs IgG and C3)		X				
TSH and Free T4		X		X 		
CD4 T cell number and LDH		X		X		X
CT scan chest, abdomen, pelvis (may use CT portion of the PET/CT) 	X			X		X
Mayo confirmation of tumor diagnosis (NHL arm only) or CLL with Richter/Hodgkin transformation	X 					
Mandatory tissue/node biopsy (see Section 17.0)	X 18, R					X 18, R
Evaluation of MRD by sensitive flow cytometry (CLL/SLL arm only)				X 		

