12. Research bone marrow aspirate specimens must be collected at the same time when clinical bone marrow tests are required (e.g. baseline, 6 and 12 months of therapy or other time when performed) and submitted. If bone marrow was performed prior to consenting the patient for this study, a repeat bone marrow is not required to obtain the research aspirate sample at baseline.
13. Adverse events, CBC, Cr and LFTs must be evaluated every cycle. For patients who tolerated therapy and have clinical benefits, they will be followed at each cycle for the first 6 months. Clinical response will be evaluated at 3 and 6 months. After 6 months of therapy, responsive or stable patients can be followed every other cycle by treating physician/provider until one or two years of total duration of therapy. However, patient will be followed by nurse at each cycle of treatment for adverse event assessment. They will be seen as needed by provider. Physical exam and tumor measurements are required only on cycles where the patient is evaluated by the treating physician. All patients who received at least 6 months of therapy and have shown clinical benefit will be evaluated again at 12 months for clinical response. For patients who continue therapy beyond 12 months, the above schedule is recommended. Further formal response evaluation is only required if there is clinical sign of disease progression. Other response evaluation is per discretion of treating physician.
14. For Follicular lymphoma grade 3 and CLL patients with Richter's transformation or Hodgkin transformation, PET/CT scan will be performed to replace CT at baseline, at 3, 6, and 12 months for response evaluation. Scans after baseline are not required for patients with lymphoplasmacytic lymphoma (Waldenstrom Macroglobulinemia) if utilizing IgM as the criteria for response. If patient had measurable nodes at baseline, then scans should be repeated.
15. For patients with lymphoplasmacytic lymphoma (Waldenstrom Macroglobulinemia) only when this is being used as the criteria for measurable disease.
16. Reticulocytes are required at baseline for all patients. After baseline may be ordered at physician discretion.
17. At 6 month visit. If there is no change from baseline, further testing is not required.

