11.5 Arm B: Low grade NHL patients

Response Considerations

Definitions for clinical response for patients with lymphoma are from the Cheson et al. Revised Response Criteria for Malignant Lymphoma (Cheson, Pfistner et al. 2007). Lymph node measurements should be taken from the CT portion of the PET/CT, or MRI scans, or dedicated CT scans where applicable. Measurement of lymphadenopathy will be determined by adding the sum of the products of the maximal perpendicular diameters of measured lesions (SPD). Measurable extranodal disease should be assessed in a manner similar to that for nodal disease. For these recommendations, the spleen is considered nodal disease. Disease that is only assessable (eg, pleural effusions, bone lesions) will be recorded as present or absent only, unless, while an abnormality is still noted by imaging studies or physical examination, it is found to be histologically and pathologically negative. Disease assessable by physical exam only (e.g. skin lymphoma) will be recorded as either measurable diseases using targeted lesions or photography at the baseline and subsequent visits for response assessment.

Response is based on CT alone or the CT component of PET/CT or MRI where applicable and the PET.

PET/CT scans are required at baseline for all Follicular lymphoma grade 3

**Follicular lymphoma grade 3** PET scans are required at response assessments for these patients. These patients should be followed by the FDG-avid or PET positive criteria (part a).

**Follicular lymphoma grade 1 or 2 and marginal zone lymphoma:** Response will be determined by CT (PET/CT or dedicated CT). These patients should be followed by the variably FDG-avid or PET negative criteria (part b).

**Waldenstrom macroglobulinemia:** For patients with Waldenstrom macroglobulinemia, response will be assessed according to Section 11.6.

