## 13.0 Treatment/Follow-up Decision at Evaluation of Patient

NOTE: Per addendum 3, for patients with Richter's transformation, treatment and follow-up decision will be based on the Richter's response criteria.

- 13.1 Arm A and Arm C: If the patient develops progressive disease (not tumor flare) at any time while on single-agent (MK-3475) therapy, or has stable disease without partial remission at the response evaluation at months 3 of the single-agent (MK-3475) therapy, a commercially available signal inhibitor can be added to MK-3475 (remain at the dose 200 mg IV every 3 weeks). If the patient develops PMD/PD at any time during active treatment with the combination of MK-3475 and a signal inhibitor or patient refuses all further study participation including refusal of observation, study treatment will be discontinued and the patient will go directly to EVENT MONITORING. Refer to Section 4.0 for required tests at PMD/PD. Patients will then be followed in event monitoring per Section 18.0.
- 13.2 Arm B : If the patient develops PD at any time during active treatment or patient refuses all further study participation including refusal of observation, study treatment will be discontinued and the patient will go directly to EVENT MONITORING. Refer to Section 4.0 for required tests at PD. Patients will then be followed in event monitoring per Section 18.0.
- 13.3 Patients not progressing on active treatment and tolerating the therapy will continue treatment per protocol for 12 months. If patient is continuing to benefit from MK-3475 treatment after 12 months, they may continue to receive treatment up to 24 months at investigator/sponsor discretion.

13.4 Observation: During observation patients will be seen every 3 months according to the test schedule in Section 4.0 for up to one year. When a subject discontinues treatment, all applicable activities scheduled for the final trial visit should be performed at the time of discontinuation. Any adverse events which are present at the time of discontinuation/withdrawal should be followed in accordance with the safety requirements outlined in Section 10.0 - Assessing and Recording Adverse Events. Patients will discontinue study treatment and go to observation for the following reasons:

- Completion of 12 months or more therapy of MK3475 or combination treatment as determined by investigator/sponsor discretion

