- An unacceptable adverse event that occurs after the patient received at least 2 cycles of treatment, which in the opinion of the Investigator, precludes further trial participation.

13.5 Event Monitoring: Patients will enter event monitoring for the following reasons:

- If the patient develops evidence of PMD/PD (For CLL Arm A and C: PMD/PD on combination therapy; For B-NHL Arm B: PD on MK-3475 single therapy) during treatment or OBSERVATION by examination, blood counts, or imaging as defined in Sections 11.23, 11.4, 11.54 and 11.61, they will be considered to have progressed and will enter EVENT MONITORING. Refer to Section 4.0 for required tests at PMD/PD.

NOTE: Patients whose only evidence of disease recurrence is by sensitive evaluation of MRD will continue under OBSERVATION in accord with standard clinical practice and will NOT be considered PD.

- Subsequent treatment for CLL or NHL
- Failure to return for an evaluation during OBSERVATION
- Patient refusal of further study treatment or noncompliance
- Patient develops an intercurrent illness that precludes further participation, or requires a prohibited concomitant treatment
- The Investigator withdraws the patient in the patient's best interests
- Administrative reasons (e.g., the patient is transferred to hospice care)
- Pregnancy
- An unacceptable adverse event that occurs during cycles 1-2

**Note:** When a subject discontinues treatment, all applicable activities scheduled for the final trial visit should be performed at the time of discontinuation. Any adverse events which are present at the time of discontinuation/withdrawal should be followed in accordance with the safety requirements outlined in Section 10.0 -Assessing and Recording Adverse Events

13.6 A patient is deemed ineligible if after registration, it is determined that at the time of registration, the patient did not satisfy each and every eligibility criteria for study entry. The patient will go directly to the event-monitoring phase of the study:

- If the patient received treatment, all data up until the point of confirmation of ineligibility must be submitted. Event monitoring will be required per Section 18.0 of the protocol.
- If the patient never received treatment, on-study material and the End of Active Treatment/Cancel Notification Form must be submitted. No further data submission is necessary.

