16.322 Treatment-free survival (TFS) for single-agent MK-3475 is defined as the time from registration to the date of initiation of subsequent treatment for CLL/SLL or lymphoma or death due to any cause. In Arm A and Arm C, the initiation of combination therapy with MK-3475 and the signal inhibitor will be considered subsequent treatment.

In Arm A and Arm C, TFS for the combination of MK-3475 and the signal inhibitor is defined as the time from initiation of combination therapy to the date of initiation of subsequent treatment for CLL/SLL or death due to any cause.

The distribution of treatment-free survival will be estimated using the method of Kaplan-Meier.

16.323 The time to next treatment (TNT) for single-agent MK-3475 is defined as the time from registration to the date of initiation of subsequent treatment for CLL/SLL or lymphoma. In Arm A and Arm C, the initiation of combination therapy with MK-3475 and the signal inhibitor will be considered subsequent treatment.

In Arm A and Arm C, TNT for the combination of MK-3475 and the signal inhibitor is defined as the time from initiation of combination therapy to the date of initiation of subsequent treatment for CLL/SLL.

The distribution of time to next treatment will be estimated using the method of Kaplan-Meier.

16.324 The complete response rate will be estimated by the number of patients who achieve a CRI or CR (Arms A and B) or CMR or CR (Arm C) divided by the total number of evaluable patients. Complete response rate will be evaluated for single-agent MK-3475 in each arm and also for the combination of MK-3475 and the signal inhibitor in Arm A and C. All evaluable patients will be used for this analysis. Exact binomial 95% confidence intervals for the true complete response rate will be calculated in each arm.

16.325 Duration of response (DR) is defined for all evaluable patients who have achieved a PR, nPR, CCR, CRI, or CR (Arms A and B) or PMR, CMR, PR or CR (Arm C) as the date at which the patient's objective status is first noted to be a PR, nPR, CCR, CRI, or CR (Arms A and B) or PMR, CMR, PR or CR (Arm C) to the earliest date relapse is documented. Duration of response will be evaluated for single-agent MK-3475 in each

arm and also for the combination of MK-3475 and the signal inhibitor in Arm A and C. The distribution of duration of response will be estimated using the method of Kaplan-Meier.

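### Schedule 4.1 sets no CT, tumor measurement, IgM or SPEP for Arm B in Observation, so relapse after treatment can be dated late and duration of response can read too long

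*Combined protocol and SAP*

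**What the plan says.** Section 4.1 schedules "Observation (every 90 days ± 14 days"), and Section 13.4 adds: "During observation patients will be seen every 3 months according to the test schedule in Section 4.0 for up to one year". In that column every arm has adverse event assessment, physical exam, CBC and chemistry. The row "Tumor measurement by physical exam (CLL/SLL arm only") is marked in Observation, but its label excludes Arm B. The row "CT scan chest, abdomen, pelvis (may use CT portion of the PET/CT") is marked at screening, response evaluation and progression, and is blank in Observation. The SPEP and immunoglobulin rows are blank there too.

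For treatment beyond 12 months, footnote 13 of 4.1 says: "Further formal response evaluation is only required if there is clinical sign of disease progression".

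Section 13.5 declares progression "during treatment or OBSERVATION by examination, blood counts, or imaging as defined in Sections 11.23, 11.4, 11.54 and 11.61". Section 11.71, which holds the Waldenstrom criteria, is not in that list.

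Section 18.1 marks the Measurement form in Observation with no arm limit, and its footnote points to Section 11 for the criteria.

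Section 16.325 runs duration of response from first response "to the earliest date relapse is documented", with no limit to time on treatment. Section 16.321 is narrower: single-agent PFS counts progression while on single-agent MK-3475, or death.

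**The concern.** What defines Arm B progression is what the schedule stops collecting once treatment ends. The CT required at progression confirms a suspicion; it does not screen for one. In indolent lymphoma, nodal growth that cannot be felt, or an IgM rise without cytopenia or symptoms, may be present for some time before anything at a 90-day visit prompts a scan or a protein test. The relapse date in 16.325 is then the date of suspicion, and duration of response reads long.

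Goal 2.22 asks for duration of response and PFS in Arm B. A patient who stops early for an adverse event after at least 2 cycles gets a response evaluation 2 to 8 weeks after the last dose (or at the next 3-, 6- or 12-month point, if sooner). Up to a year without a scheduled disease measurement then follows.

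The sections also disagree with each other. Section 18.1 expects a form for which 4.1 schedules no Arm B measurement, and 13.5 gives no route to a Waldenstrom progression.

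**Working it through.** **1. Definition against schedule, Arm B in Observation**

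| Basis for progression | Defined in | Scheduled in Observation (4.1)? |
|---|---|---|
| Node or lesion size on CT | 11.5, 11.54 | No; CT row blank |
| Palpable or skin lesions, measured | 11.5, 11.54 | Exam yes; measurement row is CLL/SLL only |
| Monoclonal IgM up 25% from nadir by electrophoresis, repeated 4 weeks apart | 11.71 | No; immunoglobulin and SPEP rows blank (SPEP is blank at progression too) |
| Waldenstrom cytopenias | 11.71 | Yes; CBC |
| Waldenstrom symptoms, bulky nodes or organs | 11.71 | In part; exam and adverse event assessment |

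**2. The plan's own Arm B figures (16.21, 16.22)**

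The rule is 5 or more responses in 23, so the probability of a positive result is P(X ≥ 5) = Σ C(23,k) p^k (1−p)^(23−k) for k = 5 to 23. At p = 0.10, 0.15, 0.20, 0.25 and 0.30 this gives 0.0731, 0.2560, 0.4993, 0.7168 and 0.8644. The plan states 0.07, 0.26, 0.50, 0.72 and 0.86, so its figures reproduce. The rule uses response while on single-agent MK-3475, so the Observation schedule does not enter it.

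Expected responders are 23 × p: 2.3 at 10%, 4.6 at 20%, 6.9 at 30%. Duration of response rests on about 2 to 7 patients.

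**3. Duration of response under assumed lags**

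The plan gives no duration figure and no detection lag. Assumptions, none from the documents: response noted at month 3; exponential time to relapse with median m; treatment stopped at month 6 or 12; CT at months 6 and 12 while on treatment; four Observation visits 3 months apart; follow-up cut at the last one, although event monitoring (18.1) runs longer. With a scan at each visit, relapse is found at the next visit. Without one, it is found only once it has been present for a lag L.

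Share of responders relapsing after a month-12 stop (9 months into response) = 0.5^(9/m): 35% for m = 6, 60% for m = 12, 71% for m = 18.

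Share of relapses documented by the end of Observation, month-12 stop (21 months into response) = 1 − 0.5^((21−L)/m). For m = 12: 70% with scans; 65%, 58% and 50% for L = 3, 6 and 9.

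Simulated Kaplan-Meier median duration in months (400,000 draws; NR = not reached):

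| Stop | True median | Scan each visit | L = 3 | L = 6 | L = 9 |
|---|---|---|---|---|---|
| Month 12 | 6 | 9 | 9 | 9 | 9 |
| Month 12 | 9 | 9 | 9 | 9 | 9 |
| Month 12 | 12 | 15 | 18 | 21 | NR |
| Month 12 | 18 | 21 | NR | NR | NR |
| Month 6 | 6 | 6 | 9 | 12 | 15 |
| Month 6 | 9 | 9 | 12 | 15 | NR |
| Month 6 | 12 | 15 | NR | NR | NR |

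Medians move in visit-sized steps, and several true medians fall exactly on a visit, so an entry can land one visit either way. The documented shares do not have that problem.

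**4. PFS in treatment months 12 to 24**

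Illustration only, for patients still on single-agent treatment and not followed by IgM. Let S(t) = 0.5^(t/m), with progressions after month 12 found L months late, so the observed curve is S(max(12, t−L)). For m = 12, S(18) = 0.354 reads 0.420 (L = 3) or 0.500 (L = 6); S(24) = 0.250 reads 0.297 or 0.354. At 18 months, m = 9 gives 0.250 against 0.315 or 0.397, and m = 18 gives 0.500 against 0.561 or 0.630. The overstatement at 18 months is 6 to 15 points.

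For scale, the 95% half-width at 0.354 with all 23 patients and no censoring is 1.96 × √(0.354 × 0.646 / 23) = 0.195, about 20 points.

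**The case against.** Several stronger readings are tempting, and the documents do not support them.

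- **Progression in Observation is found only through symptoms.** No. Exam and CBC every 90 days can show palpable nodes, enlarged organs or Waldenstrom cytopenias in a patient without symptoms, and 13.5 allows examination, counts or imaging.
- **The Observation gap lengthens PFS.** Not as written. Section 16.321 counts progression only while on single-agent MK-3475, so progression in Observation is not a PFS event. If PFS is meant in the usual sense, it would be exposed like duration of response; the text should say which.
- **Treatment months 12 to 24 are unmonitored.** No. Footnote 13 recommends continuing the earlier visit schedule, and Waldenstrom patients followed by IgM have it before each cycle (footnote 15). What is missing is a required formal evaluation without clinical signs.
- **Section 11.5 demands skin measurements in Observation.** Skin disease "will be recorded as either measurable diseases using targeted lesions or photography at the baseline and subsequent visits", but the sentence goes on to tie those visits to response assessment. It does not set an Observation measurement.
- **Arm B is singled out for missing scans.** CT is blank in Observation for every arm, including Arm C, which is assessed by PET/CT. Arms are analysed independently, so the contrast with Arm A biases no comparison.

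It is also fair that the lags are assumed, that sampling error with 23 patients is wider than the PFS shift illustrated, and that the form table in 18.1 suggests the authors did intend measurement in Observation. These points limit the size and scope of the concern. They do not remove the blank cells, the conflict between 4.1 and 18.1, the omission of 11.71 from 13.5, or the upward direction for duration of response.

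**Conclusion.** The point holds for duration of response in Arm B. Relapse after treatment has no scheduled CT, tumor measurement, IgM or SPEP, so it can be dated late, and any such error lengthens the endpoint. Only the direction comes from the documents. The size depends on the assumed lag, the stopping time and the true duration: under the assumptions shown, the median shifts by nothing (month-12 stop, true median 6 or 9 months), by up to about 9 months, or to not reached. With about 2 to 7 responders, one or two late dates can move the median.

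For PFS as defined, the concern is limited to treatment months 12 to 24 in patients not followed by IgM. The primary endpoint and the 5-of-23 rule are untouched. Whatever the size of the bias, 4.1, 13.5 and 18.1 need to be reconciled. This should be corrected, but it does not threaten the main conclusion of the trial.

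**What to change.** 1. **Schedule.** Reconcile 4.1 with 18.1 by applying the exam tumor-measurement row to Arm B at the existing Observation visits (palpable and skin lesions). For Waldenstrom patients, add IgM and SPEP to the blood already drawn, since 11.71 is written in terms of electrophoresis. Add 11.71 to the list in 13.5.
2. **Analysis.** In 16.325, and in 16.321 for treatment beyond month 12, present Arm B estimates up to each patient's last scheduled disease evaluation. That is month 12, or the evaluation 2 to 8 weeks after early stopping. Label later times as clinically detected progression. A single month-12 cut for everyone would not fit patients who stop early.
3. **Definition.** State in 16.321 whether progression after treatment stops counts as a PFS event.

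The cost is a table edit, a few measurements at exams already held, one added laboratory request for Waldenstrom patients, and a few sentences in the analysis section. Arm B duration estimates will be shorter or slightly less favourable, and ending them at an early stop assumes that stopping is unrelated to relapse risk. No CT is added, so non-palpable nodal growth stays without scheduled detection; the labelling in item 2 makes that visible. Arm B closed to accrual in April 2017, so the schedule edit may reach few patients, but items 2 and 3 need no new data.

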## 8.0 Dose modification based on Adverse Events

### 8.1 MK-3475 Dose Levels

Dose Level	MK-3475**
0*	200 mg IV Day 1 every 21 days

\*Dose level 0 refers to the starting dose.

\*\*If dose modifications are needed, the dosing interval may be increased by 7 days each time, the maximal dosing interval allowed is 8 weeks.

Note: This study will not allow dose reduction of MK-3475, only dose interval changes

8.2 Arms A and C Dose Modifications – NOTE: Dose hold/modification of Ibrutinib or Idelalisib will be based on the package insert of the individual medicine. If the patient is on a moderate cytochrome P450 inhibitor or inducer (see Appendix VII), caution is recommended and close monitoring of toxicity or efficacy of therapy is warranted. Providers should consult the package insert for recommendations on dose adjustment in the setting of drug interactions. In case an adverse event cannot be easily attributed to either MK-3475 or the signal inhibitor, strongly recommend to discuss with study chair and/or sponsor for subsequent decision.

8.3 MK-3475 Dose Modifications only-see table below. In case an adverse event cannot be easily attributed to either MK-3475 or the signal inhibitor, strongly recommend to discuss with study chair and/or sponsor for subsequent decision.

→ → Use the NCI Common Terminology Criteria for Adverse Events (CTCAE) version 4.0* unless otherwise specified ← ←			
CTCAE System/Organ/Class (SOC)	ADVERSE EVENT (at least possibly related)	AGENT	ACTION**
AT TIME OF RETREATMENT			
Gastrointestinal disorders 	Enterocolitis Grade 2	MK-3475	Hold study treatment and consider infection evaluation with C. diff toxin. If rule out c.diff, anti-diarrheal treatment should be started. The recommended dose of loperamide is 4 mg at first onset, followed by 2 mg every 2-4 hours with oral hydration until diarrhea free (maximum 16 mg/day). If symptoms are persistent for more than one week or complicated with rectal bleeding, GI consultation and endoscopy is recommended. Systemic corticosteroids or budesonide 9 mg daily should be initiated (e.g., 0.5 mg/kg/day of prednisone or equivalent). When symptoms improve to Grade 1 or less, corticosteroid taper should be started. If AE improves to grade 1 or less within 4 weeks, study treatment should be restarted at the same dose with the same cycle length for the first occurrence. The cycle

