	$\geq$ Grade 3		Discontinue treatment. Evaluation by an ophthalmologist is strongly recommended. Infectious causes will need to be ruled out. Treat with topical or systemic steroids is recommended. When symptoms improve to grade 1 or less, systemic steroid taper should be started.
Cardiac disorders	Myocarditis Grade 1	MK-3475	Hold all treatment. Consult study chair. Resume when resolved and corticosteroids have been tapered, if applicable. If not resolved within 12 weeks of last dose or if corticosteroids cannot be reduced to $\leq$ 10 mg prednisone or equivalent per day within 12 weeks, discontinue treatment and go to observation if $\geq$ 2 cycles of therapy were given, otherwise go to event monitoring. Ensure adequate evaluation to confirm etiology and/or exclude other causes. .
	$\geq$ Grade 2		Discontinue all treatment and go to observation if $\geq$ 2 cycles of therapy were given, otherwise go to event monitoring. Ensure adequate evaluation to confirm etiology and/or exclude other causes. May administer corticosteroids.

Metabolism and nutrition disorders	Glucose intolerance (Type 1 diabetes mellitus [if new onset] or Hyperglycemia Any Grade	MK-3475	Hold treatment of MK-3475. Consult with endocrinology to decide if T1DM is confirmed. If T1DM confirmed, initiate insulin replacement therapy. Administer anti-hyperglycemic in participants with hyperglycemia. Monitor for hyperglycemia or other signs and symptoms of diabetes. Prior to restarting, consult with PI or treating physician to assess whether further treatment is indicated.
------------------------------------	---	---------	--

→ → Use the NCI Common Terminology Criteria for Adverse Events (CTCAE) version 4.0* unless otherwise specified ← ←			
CTCAE System/Organ/Class (SOC)	ADVERSE EVENT (at least possibly related)	AGENT	ACTION**
AT TIME OF RETREATMENT			

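### Section 8.3 holds MK-3475 for new-onset type 1 diabetes or possibly related hyperglycemia of any grade, but neither test schedule (4.1, 4.2) includes a glucose measurement

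*Combined protocol and SAP*

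**What the plan says.** The dose-modification table in Section 8.3 has a metabolism row whose event is "Glucose intolerance (Type 1 diabetes mellitus [if new onset] or Hyperglycemia Any Grade". The column is headed "ADVERSE EVENT (at least possibly related", so the row applies only to events that meet that attribution. The action begins "Hold treatment of MK-3475. Consult with endocrinology to decide if T1DM is confirmed". After the treatment steps, the same cell adds "Monitor for hyperglycemia or other signs and symptoms of diabetes" and ends "Prior to restarting, consult with PI or treating physician to assess whether further treatment is indicated".

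The single-agent schedule in Section 4.1 has two chemistry rows:

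- "Chemistry group (SGOT [AST], SGPT [ALT], total bilirubin[T-Bil], serum creatinine, alkaline phosphatase, direct bilirubin only when T-Bil elevated", marked at screening, before each cycle from cycle 2, at response evaluations, in observation and at progression.
- "Uric acid, phosphate, calcium, potassium, sodium", marked at screening only.

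The combination-phase schedule in Section 4.2 repeats the first row without change. The per-cycle footnotes (13 in Section 4.1, 8 in Section 4.2) require adverse events, blood count, creatinine and liver tests. Section 7.2 places each dose after the assessments listed in the schedule.

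**The concern.** Hyperglycemia is a laboratory finding, and a hold that applies at any grade presupposes a measured value. If no value is scheduled, a site can follow the protocol exactly, give every dose, and never be in a position to apply the rule until symptoms appear or someone orders glucose for another reason. Dosing every three weeks could continue in the meantime.

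The missing baseline matters as well. Section 3.26 admits patients with diabetes. Steroids are allowed at entry up to 20 mg of prednisone a day (3.22), and at 0.5 to 2 mg per kg for ibrutinib withdrawal (7.4). When a raised glucose is found, the investigator must judge whether it is new and at least possibly related, with no protocol value to compare it with. The error could go either way: continued dosing through a true event, or an unnecessary hold for steroid-related or long-standing hyperglycemia.

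**Working it through.** The plan gives no figure to reproduce. The check compares the hold rule with every place where a glucose test could be scheduled, then counts the draws affected.

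**Where glucose could appear**

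- Eligibility labs (3.19): creatinine, platelets, neutrophils, bilirubin, AST or ALT. No glucose.
- Screening in 4.1: the itemised chemistry row and the electrolyte row. No glucose.
- Before each cycle in 4.1 and 4.2: the itemised chemistry row and the footnote minimum. No glucose.
- Combination-phase baseline: Section 4.2 has no baseline column. Its footnote 1 takes the values obtained after the last single-agent cycle, and footnote 19 of Section 4.1 makes the progression visit the baseline for patients who move on. In practice this is the month-3 evaluation (stable disease) or the progression visit. Both use the 4.1 chemistry row. No glucose.

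Because the chemistry row names its contents, glucose cannot be read in as part of an unspecified panel. By contrast, Section 4.1 does schedule TSH and free T4 at screening and month 6, which serves the thyroid events in Section 8.3.

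**Draws that precede a dose**

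Inputs: 21-day cycles, 17 cycles in 12 months without delays, and treatment allowed up to 24 months (7.6).

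- Single agent, 12 months: draws before cycles 2 to 17 = 17 − 1 = 16. With glucose: 0.
- Switch to combination after cycle 4, 12 months in total: 4 + 13 = 17 cycles. Draws = 3 (before cycles 2 to 4) + 1 (month-3 evaluation, before the first combination dose) + 12 (before combination cycles 2 to 13) = 16. With glucose: 0.
- Treatment to 24 months at the same rate: 2 × 17 = 34 cycles, so 34 − 1 = 33 draws. With glucose: 0.

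The screening draw is not counted here. It would supply the baseline.

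**Scale of the listed risk**

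Section 15.17 lists type 1 diabetes at 0.1% to under 1%. Arm C, the only arm not marked closed to accrual, plans 20 patients (16.12). Assuming that rate applies and patients are independent:

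- Expected cases: 20 × 0.001 = 0.02, to under 20 × 0.01 = 0.2.
- Chance of at least one: 1 − 0.999^20 = 2.0%, to under 1 − 0.99^20 = 18.2%.

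This is the chance that a case occurs, not that it goes undetected. The documents give no rate for hyperglycemia of any grade, which is the other trigger.

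**The case against.** The best defence is that the protocol relies on clinical detection for most immune events, and that this is a legitimate choice. Adrenal events, pituitary events (beyond TSH and free T4), myocarditis and uveitis have no dedicated scheduled test either. Patients are told to report any side effect (15.191). Section 15.196 lists vague fatigue and nausea as reasons to order labs, although it does not name diabetes. Adverse events are assessed every cycle. Medical history at screening, and concomitant medications from 28 days before the first dose (9.4), should document known diabetes and steroid use. Nothing prevents routine-care glucose testing. The 8.3 sentence on monitoring for hyperglycemia can also fairly be read as a standing instruction rather than one that starts only after a hold.

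Most of this stands, and it keeps the point small. It does not close the gap. Read as a standing instruction, the 8.3 sentence still names no test and no time. History and medication records are not a glucose value. Glucose differs from the other untested events because hyperglycemia is defined by a laboratory value and the blood is already drawn before every cycle from cycle 2.

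Two stronger readings are tempting, and the documents do not support them. A reader might infer from the routine reporting table in Section 10.6, which lists no glucose-related term, that hyperglycemia would go unreported. Section 10.61 requires submission of unlisted Grade 2 events that are at least possibly related, and of all Grade 3 and 4 events regardless of attribution. The gap is in detection, not in reporting what is found. A reader might also infer that the 8.3 rule must be rewritten for patients who enter with diabetes, for instance to act only on a rise in grade. The row already carries an attribution condition, a new-onset qualifier for type 1 diabetes and a consult before restart. A grade-rise rule for those patients would also leave out someone with normal screening glucose who later receives steroids at 1 to 2 mg/kg for an immune event.

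**Conclusion.** The point holds as a minor safety-monitoring gap. A stated hold has no scheduled measurement behind it: none of the 16 pre-cycle draws over 12 months, or of about 33 over 24 months, includes glucose, and no baseline value is collected. The counts assume 21-day cycles without delays; longer intervals would reduce them, but the number with glucose stays at zero.

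A reader might go further and infer that cases of diabetes are being missed. The documents do not show that. They give no rate of missed events, and symptoms, adverse event assessment and unscheduled labs remain as routes to detection. The primary response analysis is unaffected, because a glucose result plays no part in the definition of response.

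**What to change.** Add glucose to the Chemistry group row in both schedules:

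- Section 4.1: at screening, before each cycle, and at the month-3 or progression visit that serves as the combination-phase baseline.
- Section 4.2: before each combination cycle.

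Record with each value whether the sample was fasting and the current steroid dose. Leave the 8.3 hold rule and its attribution condition unchanged; the investigator would use the baseline value when judging relatedness.

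The cost is one more analyte on samples already taken, an edit to two tables, and the recording of two short items. The downside is some extra low-grade findings, endocrinology consults and short holds. Some will come from permitted steroids, from steroids given for immune-related events, or from non-fasting samples. The recorded fasting status and steroid dose should help the investigator recognise these, but will not remove them.
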